### **8.7.2 Reporting of Safety Events to FDA**

The artificial sweeteners (sucralose and acesulfame potassium) in the sugar-free water enhancers are considered food additives by the US FDA. If there are any adverse events observed during or after the study, the study staff will report them to the FDA by phone at [contact], which is the FDA Center for Food Safety and Applied Nutrition reporting hotline phone number. There is also the option to submit a Medwatch form at <https://www.fda.gov/safety/report-problem-fda/how-report-non-emergency#food>. We will report adverse events using whichever methods is available to the PI at the time of reporting.

### **8.7.3 Reporting of Pregnancy**

There are no specific pregnancy-related policies and procedures.

## **8.8 Halting Rules**

If there is a significant number of children who experience symptoms or side effects that are thought to be associated with the sugar-free water enhancers (more than 20%), an ad hoc safety review will be convened. The objective of the safety review is to decide whether the study (or intervention for an individual or study cohort) should continue per protocol, proceed with caution, be further investigated, be discontinued, or be modified and then proceed. Suspension of enrollment (for a particular group, a particular study site, or for the entire study) is a potential outcome of a safety review.

## **STUDY OVERSIGHT**

In addition to the PI's responsibility for oversight, study oversight will be under the direction of a Data and Safety Monitoring Board (DSMB) appointed by the NIDCR. The DSMB will operate under the rules of an NIDCR-approved charter that will be approved at the organizational meeting of the DSMB. The conduct of the DSMB and rules regarding how often the Board will meet will be defined by the DSMB charter for the study. At this time, most data elements that the DSMB needs to assess will be clearly defined. It is anticipated that the DSMB will meet at least once per year via teleconference to assess safety and efficacy data, study progress, and data integrity for the study. If safety concerns arise, more frequent meetings may be held. The DSMB will operate under the rules of an NIDCR-approved charter that will be approved at the organizational meeting of the DSMB. At this time, most data elements that the DSMB needs to assess will be clearly defined. The DSMB will provide recommendations to the NIDCR.

## CLINICAL SITE MONITORING

Clinical site monitoring is conducted to ensure that the rights of human subjects are protected, that the study is implemented in accordance with the protocol and/or other operating procedures, and that the quality and integrity of study data and data collection methods are maintained. Monitoring for this study will be performed by the NIDCR's Clinical Research Operations and Management Support (CROMS) contractor. The monitor will evaluate study processes and documentation based on the International Council for Harmonisation (ICH), E6: Good Clinical Practice guidelines (GCP).

Details of clinical site monitoring will be documented in a Clinical Monitoring Plan (CMP). The CMP will specify the frequency of monitoring, monitoring procedures, the level of clinical site monitoring activities (e.g., the percentage of participant data to be reviewed), and the distribution of monitoring reports. Some monitoring activities may be performed remotely, while others will take place at the study site(s). Staff from CROMS will conduct monitoring activities and provide reports of the findings and associated action items in accordance with the details described in the CMP. Documentation of monitoring activities and findings will be provided to the site study team, the study PIs, NIDCR-OCTOM, and NIDCR Program staff. The NIDCR reserves the right to conduct independent clinical site monitoring as necessary.

## STATISTICAL CONSIDERATIONS

### 11.1 Study Hypotheses

#### 11.1.1 Primary Hypotheses

1. Children in the intervention arm will have lower added sugar intake from baseline to 6 months compared to children in the no-treatment control arm (measured through hair biomarker).

Null hypothesis: The average change (reduction) in added sugar intake between baseline and 6 months will be the same for children in the intervention arm and no-treatment control arm.

Alternative hypothesis: The average change (reduction) in added sugar intake between baseline and 6 months will be different for children in the intervention arm and no-treatment control arm.

#### 11.1.2 Secondary Hypotheses

1. Caregivers in the intervention arm will have lower added sugar intake from baseline to 6 months compared to caregivers in the no-treatment control arm (measured through hair biomarker).
2. Children in the intervention arm will have sustained lower added sugar intake 6 months after the end of the intervention as compared to children in the no-treatment control arm.

#### 11.1.3 Exploratory Hypotheses

1. Caregivers in the intervention arm will have greater improvement in knowledge, beliefs, and self-efficacy related to oral health, sugar-free drinks, and ability to help their children switch from sugared to sugar-free drinks at the end of the intervention as compared to caregivers in the non-treatment control arm.
2. Children in the intervention arm will have an altered oral microbiome, due to changes in sugared fruit drink and added sugar intake, as measured by mutans

streptococci levels and oral microbiome features through analysis of oral plaque samples.

3. Children in the intervention arm will have lower sugared fruit drink intake after receiving the intervention compared to children in the no-treatment control arm.

Null hypothesis: The average sugared fruit drink intake in ounces at 6 months and 12 months will be the same for children in the intervention arm and no-treatment control arm.

Alternative hypothesis: The average sugared fruit drink intake in ounces at 6 months and 12 months will be different for children in the intervention arm and no-treatment control arm.

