## 2.3 Exploratory

Objective	Brief Description/Justification of Outcome Measure	Outcome Measured By	Time Frame
To identify potential mechanisms associated with changes in sugared fruit drink and added sugar intake.	Behavioral survey questions to assess changes in caregiver knowledge, beliefs, and self-efficacy (see Manual of Procedures). The intervention is expected to change some of these behavioral factors, which could explain why the intervention works for some and not others.	Fruit drink survey completed by caregiver (one for each child). Obtained by trained UW study staff. In case of Covid-19 restrictions, the fruit drink survey may be conducted via phone by UW study staff or collected in person using precautions.	Baseline to 6 months.
To investigate how diet contributes to added sugar intake among child participants.	24 hour food recall data will be used to assess sugared fruit drink intake and to identify other dietary factors related to the primary outcome, added sugar intake.	Sugared fruit drink and food intake will be measured through 24 hour dietary recall interviews with caregivers, for each child at baseline and 1-month; a validated dietary intake measure using the Nutrition Data System for Research (NDSR).	Baseline, 1 month
To test the hypothesis that children in the intervention arm will have lower sugar fruit drink consumption after receiving the intervention, compared to children in the no-treatment control arm.	Beverage intake questionnaires will be used to assess sugared fruit drink intake (servings per day) among child participants.	Sugared fruit drink intake will be measured using validated beverage intake questionnaires (BEVQ-15) at 6-months and 12-months; which will be administered to caregivers to provide responses, for each child.	6 months and 12 months

Objective	Brief Description/Justification of Outcome Measure	Outcome Measured By	Time Frame
To assess for potential changes in mutans streptococci levels associated with the intervention.	Changes in mutans streptococci levels and oral microbiome features will be measured through analysis of oral plaque samples collected from children enrolled in the study.	A measure of mutans streptococci level will provide a proxy for microbiological changes associated with changes in sugared fruit drink and added sugar intake.	Baseline, 1 month, 3 months, 6 months and 12 months.  Samples will be banked and securely stored until there is funding for these analyses.

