## STUDY DESIGN

This is a 2-arm community-based behavioral trial. Participants, interventionists, investigators, and outcomes data collection staff will not be masked because it is not feasible. Data processors will be masked. While attempts will be made to mask the analyst, it will likely not be effective because of the different sizes of the intervention and control groups.

There is a total of 3 study communities (2 in the intervention arm and 1 in the no-treatment control arm). The 3 communities are located in Alaska's YK Delta, about an hour by airplane from Bethel. The 2 communities in the intervention arm are about 15-minutes away from each other by airplane. The community in the control arm is about 45 minutes away from the 2 communities in the intervention arm, which will help to minimize contamination between the control and the 2 treatment arms.

Two communities will be in the intervention arm and one community in the control arm. Allocation to the intervention arm was based on the order in which communities were ready to participate in the study as assessed during recruitment of communities. Randomizing at the community-level would have required a sample size that is beyond the scope of the current study budget. Randomizing at the family- or child-levels would not have been possible because of the small size of study communities and high risk of contamination between families or among children from the same family.

The focus is on Yup'ik Alaska Native communities because of the high rates of added sugar intake and tooth decay. Children are the focus of the primary outcome measure based on the potential for a lifetime of benefit associated with reduced added sugar intake. Outcomes will also be measured at the caregiver and community levels.

Enrollment is expected to take 1 month. Study participation will last 1 year.

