#### **4.4 Treatment Assignment Procedures**

Children in Communities A and B will be assigned to the intervention arm. Communities A and B are the first 2 communities that were recruited to be part of the study. Children in Community C will be assigned to the no-treatment control arm. Community C is the third community that was recruited to be part of the study. The study team made treatment assignment determinations as communities were recruited for the study.

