### 13.1 Final Analysis Plan

The analysis will be based on the intent to treat principle. Demographic variables will be summarized for the intervention arm and no-treatment arm at baseline and at each follow-up for all outcome measures and behavioral survey variables, as well as baseline demographics. Quantitative measures will be summarized by the mean and standard (or median and interquartile range for measures with a skewed distribution) and categorical measures will be summarized by frequency and percentage.

Linear regression analyses will be used to test if the average change in added sugar intake between baseline and 6 months is the same for children in the intervention arm and no-treatment control arm. A 2-sided 0.025 significance level will be used for the tests of the primary outcome. Generalized estimating equation (GEE) methodology will be used to fit the linear regression models using robust standard errors that account for potential clustering of outcomes within a household and allow for heteroscedasticity (Hardin and Hilbe 2003). Additional linear regression analyses will compare the 2 arms adjusted for baseline characteristics to assess for potential confounding and to assess for moderation of the intervention effect on child sugar intake by baseline characteristics, including child age, child sex, and traditional diet. In addition, to assess the effects of sex as a biological variable, separate estimates for the intervention effect on added sugar intake will be reported by child sex.

Similar linear regression analyses will be performed for the secondary outcomes for changes in caregivers' added sugar intake, knowledge, beliefs and self-efficacy. Outcomes at 1 month and 3 months will be summarized to elucidate the changes from baseline to 6 months in the intervention arm and no-treatment arm. Linear regression analyses will also be used to test the exploratory hypothesis that children in the intervention arm will have decreased sugared fruit drink intake after having received the intervention (at 6 months and 12 months).

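### The 6- and 12-month fruit drink test compares follow-up levels between non-randomised communities, and Section 13.1 names no baseline intake term for it

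*Combined protocol and SAP*

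**What the plan says.** Section 11.1.3 states the null for exploratory hypothesis 3 on levels: "The average sugared fruit drink intake in ounces at 6 months and 12 months will be the same" in the two arms. Section 11.1.1 states the primary null on change: "The average change (reduction) in added sugar intake between baseline and 6 months will be the same". The 12-month added sugar test in Section 13.1 is also on change from baseline.

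The arms were not formed by randomisation. Study Design says "Allocation to the intervention arm was based on the order in which communities were ready to participate", Section 4.4 adds "The study team made treatment assignment determinations as communities were recruited for the study", and Section 4.4.1 marks randomisation as not applicable. Two communities receive the intervention and one is the control.

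Section 13.1 gives this test one sentence, which begins "Linear regression analyses will also be used to test the exploratory hypothesis that children in the intervention arm". It specifies linear regression at 6 and 12 months and nothing about baseline intake. Earlier in the same section, in the paragraph on added sugar, stands: "Additional linear regression analyses will compare the 2 arms adjusted for baseline characteristics to assess for potential confounding". The characteristics named there are child age, child sex and traditional diet.

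On measurement, Section 2.3 says "Sugared fruit drink intake will be measured using validated beverage intake questionnaires (BEVQ-15) at 6-months and 12-months". The baseline visit in Section 6.2 and the baseline list in Section 7.1 include a 24-hour recall for each enrolled child and do not list the beverage questionnaire. Appendix A, however, marks baseline in a combined row that contains the recall, the food survey, the hair survey and the beverage questionnaire.

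**The concern.** Without randomisation, nothing in the design makes baseline fruit drink intake similar across arms. A change score or a baseline covariate is the usual partial protection. The hair outcomes have the first; this outcome, as written, has neither.

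If Community C already drank more than Communities A and B and the difference persisted, an unadjusted comparison would overstate the intervention effect. If Community C drank less, the comparison would hide or understate a real effect. With one control community, the data at 6 and 12 months alone cannot separate the two explanations.

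This test matters more than most exploratory ones. It is the plan's 6- and 12-month comparison of the behaviour the intervention targets, and the Rationale (Section 1.1.1) puts lower fruit drink intake in the main study hypothesis.

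**Working it through.** The plan states no power, SD, effect size or significance level for this test, so there is no figure of its own to reproduce. The calculation below only shows how sensitive a follow-up-only comparison is to a baseline gap.

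**Inputs from Sample Size Considerations:** 136 and 56 children; attrition 15% to 25% by 6 months; 2.15 ± 1.23 children per household; intra-family correlation (IFC) 0.3, or 0.5 as the high value.

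**Assumptions, not in the documents:** two-sided 0.05; no true effect; equal SDs; a gap of 0.2 or 0.3 SD; the 6-month attrition range also used at 12 months.

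**Step 1, effective sample size.** CV = 1.23/2.15 = 0.572. Design effect = 1 + ((CV² + 1) × 2.15 − 1) × IFC.
- IFC 0.3: 1 + (1.327 × 2.15 − 1) × 0.3 = 1.56.
- IFC 0.5: 1 + (1.327 × 2.15 − 1) × 0.5 = 1.93.

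Effective n = N × (1 − attrition) / design effect, and SE = √(1/n₁ + 1/n₂) in SD units.

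**Step 2, rejection rate with no true effect** (two-sided noncentral t with noncentrality gap/SE):

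| Attrition, IFC | Effective n | SE | Gap 0 | Gap 0.2 | Gap 0.3 | 60% of 0.3 (0.18) |
|---|---|---|---|---|---|---|
| 15%, 0.3 | 74.3 / 30.6 | 0.215 | 5% | 15.2% | 28.3% | 13.2% |
| 25%, 0.5 | 52.9 / 21.8 | 0.254 | 5% | 12.1% | 21.4% | 10.7% |

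If 60% of a 0.2 SD gap persists (0.12 SD), the rate is about 8-9%.

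**Step 3, what a baseline covariate would remove.** With within-arm correlation r between covariate and outcome, the bias left is (gap on outcome) − r × (gap on covariate), and the SE shrinks by √(1 − r²). The plan gives r = 0.6 for hair between baseline and 6 months. For a one-day recall against a questionnaire, r = 0.3 is assumed. For a 0.3 SD gap on the outcome:
- Same gap on the covariate, r = 0.6: 0.3 − 0.18 = 0.12 SD, so 40% of the bias stays; rejection is about 9-11%.
- Same gap on the covariate, r = 0.3: 0.3 − 0.09 = 0.21 SD, so 70% stays; rejection is about 14-17%.
- Half the gap on the covariate (0.15 SD): 0.21 SD at r = 0.6 and 0.255 SD at r = 0.3, so 70% to 85% stays.

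**Step 4, which baseline measure is available.** The recall is planned for every enrolled child at baseline. Recalls at 6 and 12 months are optional, so a recall-based change score is not assured. A BEVQ-15 change score depends on whether Appendix A or the visit text is followed at baseline.

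**The case against.** The strongest reply is that the adjusted models in Section 13.1 may already cover this test. The fruit drink sentence says regression will also be used, after models adjusted for baseline characteristics have been described for comparing the two arms. That reading is possible. But those models are called additional and sit in the added sugar paragraph. Even if they carry over, the characteristics named do not include baseline fruit drink intake. A reader might infer that no adjustment at all is planned, or that the confounders are wholly unspecified; the text supports neither.

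Section 13.1 also speaks of decreased intake, which hints at change, but it specifies no baseline or change score. The descriptive plan, "Demographic variables will be summarized for the intervention arm and no-treatment arm at baseline and at each follow-up for all outcome measures", might bring a baseline gap to light but would not take it out of the test.

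A reader might also infer that no baseline BEVQ-15 exists. The documents do not settle this: Appendix A read literally schedules it, and Sections 6.2 and 7.1 do not list it.

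Two further objections stand in part. The hypothesis is exploratory, which limits the consequences. And a one-day recall on a different instrument adjusts only partly, as Step 3 shows. That argues for stating the limit, not for leaving out a covariate that is already being collected.

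**Conclusion.** The point holds as a gap in the specification of one exploratory test. The comparison is of follow-up levels between communities assigned by readiness, and no baseline intake term is named for it. Under the stated assumptions, a fully persisting gap of 0.2 to 0.3 SD raises rejection with no true effect from 5% to between 12% and 28%; partial persistence lowers this considerably. Gap size, persistence, significance level and r are all assumptions.

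A reader might infer that the communities do differ at baseline, or that the trial's main conclusion is at risk. The documents show no such gap, the bias could run either way, and the primary hair-biomarker change analysis is unaffected.

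A reader might also infer that the power statement on sustained fruit drink reduction in Sample Size Considerations has no hypothesis behind it. Section 13.1 does state a secondary hypothesis of sustained reductions in both fruit drink and added sugar intake. However, Section 11.1.2 and the 12-month change test in Section 13.1 cover added sugar only. These three places need reconciling together.

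**What to change.** 1. In Section 13.1, pre-specify baseline sugared fruit drink intake as a covariate in the 6- and 12-month BEVQ-15 models. Use the baseline 24-hour recall, or the baseline BEVQ-15 if it was collected.
2. Reconcile Appendix A with Sections 6.2 and 7.1 on whether the beverage questionnaire is given at baseline, since this decides which covariate applies.
3. Report baseline intake by community, and give the unadjusted difference beside the adjusted one.
4. State that, with one control community and a one-day recall on a different instrument, adjustment reduces confounding but does not remove it, and that the result remains exploratory.
5. Reconcile Section 11.1.2, the 12-month power statement and the secondary hypothesis in Section 13.1 on whether sustained fruit drink reduction is a tested hypothesis.

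The cost is a few sentences of text. The recall is already planned for each enrolled child, so no new data collection is needed.

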## SAMPLE SIZE CONSIDERATIONS

There are about 127, 175, and 108 children ages 1 to 11 years in communities A, B, and C respectively. Some are siblings or relatives living in the same home. Based on a survey of 123 households in the 3 study communities, for the power calculations, each household was assumed to have an average of  $2.15 \pm 1.23$  children per household. In addition, to account for the clustering of children within households, a conservative intra-family correlation (IFC) of 0.3 was assumed, but an IFC as high as 0.5 was assumed to assess the effect on power (Eldridge et al. 2006).

Participation in previous studies has been over 60%. Based on our pilot study, it is feasible and reasonable to enroll at least 50% of eligible children. Communities A and B will be in the intervention arm (expected N=136) and community C will be in the control arm (expected N=56). For the power determination, a 15% to 25% attrition rate was estimated by 6 months, but it is expected that actual attrition will be less than 10% by the 6-month follow-up.

Power is determined for comparing the average reduction from baseline to 6 months between children in the intervention arm and no-treatment control arm for the primary outcome: added sugar intake per day (determined by hair samples). Based on pilot data from 54 Yup'ik children ages 6 to 17 years, the mean $\pm$ SD baseline added sugar intake, as measured by hair samples, is expected to be  $193.0 \pm 43.6$  grams per day. (Chi et al. 2015). A correlation of 0.6 is assumed between the measures at baseline and 6 months to determine the standard deviation for reduction from baseline to 6 months.

The power is calculated using a 2-sided significance level of alpha=0.025 to control the type I error for the testing of the primary outcome, and using a 2-sample t-test to compare the average reduction between the intervention arm and no-treatment control arm using the expected (unequal) sample sizes and adjusted for the IFC and attrition (Eldridge et al. 2006).

In the intervention arm, added sugar intake is expected to drop by 20% to 40%. Minimal changes are expected in the control arm, but for the power calculations have assumed modest reductions in the control arm. These estimates are based on a previous beverage substitution RCT that showed 88% reduction in the intervention group for the number of sugared beverages consumed per day and 3 school-based studies showing 20% to 26% reductions in the intervention groups (Ebbeling et al. 2012; James et al. 2004; Sichieri et al. 2014; Singh et al. 2009).

The power to demonstrate a difference between the intervention arm and control arm for the reduction from baseline to 6 months of added sugar intake is reported in the Table below. Power is high (>85%) for the majority of scenarios. For example, power is 98% to demonstrate an intervention effect for added sugar intake assuming a 30% reduction in the intervention arm and a 5% reduction in the control arm.

Table. Power to demonstrate a difference between the intervention and control groups for a reduction from baseline to 6 months in added sugar intake at a 2-sided alpha = 0.025 significance level.

Added sugar intake			
% Reduction		Power	
Intervention	Control	IFC=0.3	(IFC=0.5)
40%	5%	99%	(99%)
30%	5%	98%	(95%)
20%	1%	86%	(76%)
40%	10%	99%	(99%)
30%	10%	89%	(81%)
20%	2%	81%	(71%)

The expected numbers of children in the intervention arm and control arm will provide adequate power to test secondary hypotheses about a sustained reduction in sugared fruit drink intake and added sugar intake 6 months after the end of the intervention for children in the intervention arm. Based on a 2-sided 0.05 significance level, the power is >80% to detect a difference of 0.60 standard deviation units in the change from baseline to 12 months between the two arms. For example, power is 88% to demonstrate an intervention effect for a 20% reduction in the intervention arm versus a 2% reduction in the control arm for added sugar intake. The expected number of caregivers in the intervention arm is N=51 and in the control arm is N=21, and these sample sizes also provide adequate power to the test secondary hypothesis about a greater reduction in added sugar intake at the end of the intervention for caregivers in the intervention arm as compared to the control arm. Based on a 2-sided 0.05 significance level, the power is >80% to detect a difference of 0.75 standard deviation units in the change from baseline to 6 months between the 2 arms. For example, power is 81% to demonstrate an intervention effect for a 25% reduction in the intervention arm versus a 5% reduction in the control for the caregiver's added sugar intake.

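### The stated baseline-to-6-month correlation of 0.6 does not reproduce the 6-month power table: with equal SDs, seven cells printed as 71–95% come out at 88.5–99.8%

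*Combined protocol and SAP*

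**What the plan says.** All of this is in Sample Size Considerations.

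- Primary comparison: the change in added sugar intake from baseline to 6 months, "using a 2-sided significance level of alpha=0.025" and "using a 2-sample t-test to compare the average reduction between the intervention arm and no-treatment control arm".
- Expected numbers: 136 children in the intervention arm and 56 in the control arm.
- Baseline intake: 193.0 ± 43.6 g/day.
- SD of change: "A correlation of 0.6 is assumed between the measures at baseline and 6 months", and this is said to determine the SD of the reduction. No 6-month SD is given.
- Clustering: 2.15 ± 1.23 children per household, with an intra-family correlation (IFC) of 0.3, or 0.5 as a harsher case.
- Loss to follow-up: "a 15% to 25% attrition rate was estimated by 6 months". The single rate used for the table is not given.

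The table then gives "Power to demonstrate a difference between the intervention and control groups for a reduction from baseline to 6 months in added sugar intake" for six pairs of percentage reductions at each IFC. Four of the twelve cells are printed as 99%. The other eight run from 71% to 98%.

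The paragraph after the table gives two 12-month figures at two-sided alpha 0.05: power above 80% for a difference of 0.60 SD, and "power is 88% to demonstrate an intervention effect for a 20% reduction in the intervention arm versus a 2% reduction in the control arm". It states no correlation, attrition or IFC for 12 months.

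**The concern.** The SD of change is the planning figure on which the primary power calculation turns. The plan states enough inputs for a reader to rebuild the table, apart from the 6-month SD and the exact attrition rate. When it is rebuilt, text and table imply different SDs of change: 39 g from the text and about 48–51 g from the table. The primary power justification therefore cannot be reproduced as written. Anyone reusing these inputs, for example to judge the effect of lower enrolment, would get different answers depending on which part of the section they relied on.

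**Working it through.** **Inputs.** All are from Sample Size Considerations, as listed above. One assumption is added: the 6-month SD equals the baseline SD.

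**SD of change.** 43.6 × √(2 × (1 − 0.6)) = 39.0 g.

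**Design effect with varying household size.** CV = 1.23/2.15 = 0.572. DE = 1 + ((CV² + 1) × 2.15 − 1) × IFC, which is 1.556 at IFC 0.3 and 1.927 at IFC 0.5.

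**Effective n per arm.** N × (1 − attrition)/DE.

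**Power.** Two-sample noncentral t, with difference = 193.0 × (gap in percentage reduction).

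**One cell in full** (20% v 2%, IFC 0.3, 25% attrition):
- Difference = 193.0 × 0.18 = 34.74 g.
- Effective n = 136 × 0.75/1.556 = 65.5 and 56 × 0.75/1.556 = 27.0.
- Standard error = 39.0 × √(1/65.5 + 1/27.0) = 8.92 g.
- Noncentrality = 34.74/8.92 = 3.89.
- Power at two-sided alpha 0.025 = 94.5%. The table prints 81%.

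**The eight cells printed below 99%**, at r = 0.6 and 25% to 15% attrition:

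| Reductions | IFC 0.3: computed | Printed | IFC 0.5: computed | Printed |
|---|---|---|---|---|
| 30% v 5% | 99.9–100% | 98% | 99.4–99.8% | 95% |
| 20% v 1% | 96.5–98.1% | 86% | 91.8–94.9% | 76% |
| 30% v 10% | 97.9–99.0% | 89% | 94.3–96.7% | 81% |
| 20% v 2% | 94.5–96.8% | 81% | 88.5–92.3% | 71% |

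Seven cells differ by 4.4 points (99.4 − 95) to 21.3 points (92.3 − 71). The eighth, 30% v 5% at IFC 0.3, is within about 2 points, as are the four cells printed as 99%.

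**What does reproduce the table.** One SD of change rounds to all eight printed values at each attrition rate. With equal SDs, r = 1 − SD²/(2 × 43.6²).

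| Attrition | SD of change | Implied r (equal SDs) | 6-month SD needed if r = 0.6 |
|---|---|---|---|
| 15% | about 51 g | about 0.31 | 63.4 g |
| 20% | about 49.5 g | about 0.36 | 61.2 g |
| 25% | about 48 g | about 0.40 | 58.9 g |

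The last column solves 43.6² + s² − 2 × 0.6 × 43.6 × s = SD² for s.

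**Other explanations tried at r = 0.6.**
- Attrition: matching the eight cells needs about 49–51% loss, against the stated 15–25%.
- Design effect without the CV term: this raises the effective n and widens the gap.
- Normal in place of t: no match.
- Smaller alpha: even 0.005 with 25% attrition brings only 6 of the 12 cells within 2 points.
- 6-month SD shrinking in proportion to the mean: the seven cells are 89.2–99.9%.

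**12-month figures** (alpha 0.05, IFC 0.3). The SDs of change that fit the 6-month table give about 88% for 20% v 2%, in line with the printed example. The 0.60 SD statement needs no mean, SD or correlation. The same effective n gives 79.0%, 76.5% and 73.7% at 15%, 20% and 25% attrition, against the printed figure of more than 80%.

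**The case against.** The strongest reply is that the contradiction is conditional. The plan states no 6-month SD, and section 13.1 allows for heteroscedasticity, so equal SDs are the reviewer's assumption. That stands: strictly, what is shown is that the text and table disagree unless the 6-month SD is about 59–63 g. But that is 35–45% above baseline (58.9/43.6 = 1.35; 63.4/43.6 = 1.45) while mean intake is expected to fall, and nothing in the plan says so.

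Some stronger readings are tempting, and the documents do not support them.

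- *The study is underpowered.* With the stated correlation and equal SDs, power is higher than printed in every discrepant cell. If the table is the intended calculation, its powers stand.
- *Attrition was 20%, so the true correlation was 0.36.* The plan says "The expected number of caregivers in the intervention arm is N=51 and in the control arm is N=21". Those numbers fit 20% attrition (136 × 0.80/2.15 = 50.6; 56 × 0.80/2.15 = 20.8). They fit 25% with two children per household equally well (136 × 0.75/2 = 51; 56 × 0.75/2 = 21). The derivation is not given, so neither the rate nor the correlation is established.
- *0.6 was entered in place of 1 − 0.6.* That gives 43.6 × √(2 × 0.6) = 47.8 g and matches the table at 25% attrition. It is a possible source, no more.
- *The 88% at 12 months is wrong.* The 0.6 is stated for baseline to 6 months only. A lower correlation over a longer interval would be unremarkable, so the 88% contradicts nothing stated.

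It is also fair to say that the model used here does not recover the 0.60 SD statement, so the inputs behind the 12-month paragraph are not fully known. A larger effective n would not rescue the 0.6 at 6 months, since it would raise power further above the table.

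**Conclusion.** The point holds in this form. Given equal SDs at baseline and 6 months, the stated correlation of 0.6 and the printed 6-month table cannot both be right. Seven cells are off by about 4 to 21 points, and no attrition in the stated range explains the gap. The table corresponds to an SD of change of about 48–51 g, not 39.0 g.

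Confidence is high that the table is not reproduced under equal SDs. It is not high for any particular replacement correlation, because the attrition rate behind the table is unknown. The 12-month figures need their inputs stated and a recheck, but are not shown to be wrong. The consequence is limited to documentation of the primary power justification: the discrepancy is conservative if 0.6 is right, and sample size, test and alpha do not change.

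**What to change.** In Sample Size Considerations, state the correlation, the 6-month SD and the single attrition rate used for the table, and make the text and table agree. Depending on what was actually done, one of the following applies:

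- Correct the stated correlation to the value behind the table (about 0.31–0.40, depending on attrition).
- Keep 0.6 and state the larger 6-month SD, with its basis.
- If 0.6 with equal SDs was intended, recompute the table.

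For the 12-month paragraph, state the correlation, attrition and IFC used, then recheck both the 88% example and the claim of more than 80% power for 0.60 SD. The 88% should not be replaced unless 0.6 is confirmed to apply at 12 months.

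The cost is wording and a recalculation. No participants are added, and the test, alpha and analysis are unchanged.
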